Approximately 15% patients undergoing PCI have HBR and are generally excluded or underrepresented in the DES trials.^{13, 14} These patients will benefit from shorter duration of DAPT. However, contemporary clinical trials are done with newer stent designs (polymer-free)¹³ include older adults with no inclusion criteria that denote HBR¹⁵ or have prespecified subgroup with HBR¹⁶ significantly limiting the generalizability. The decline in the rates of stent thrombosis with newer generation stents coupled with paucity of data to guide clinical decision-making in this high-risk group highlights the importance to develop simple treatment protocols to lower their bleeding risk. Early bleeding hazard with aspirin coupled with time-dependent increase in major bleeding events underscores the need to aggressively deescalate DAPT, albeit not at the expense of heightened ischemic risk. Such reduction in concomitant ischemic events can be achieved with genotype guidance. A post-hoc analyses of TAILOR PCI demonstrated an almost 80% risk reduction for ischemic events with genotype guidance in the first 3 months after PCI, the highest risk period following PCI. Potential advantages of genotype-guided P2Y₁₂ inhibitor therapy in which a large number of patients receive clopidogrel (given an approximate 50% to 70% prevalence of *CYP2C19* noncarriers) and the remainder receive more potent alternative P2Y₁₂ inhibitors is lower cost and lower risk for bleeding for this group as compared with patients receiving either ticagrelor or prasugrel. Furthermore, reduction in ischemic events with newer P2Y12 inhibitors could only be demonstrated among *CYP2C19* loss-of-function (LOF) carriers, underscoring the utility of upfront genetic testing prior to routine DAPT prescription in patients with HBR undergoing PCI. Our specific aims of the present pilot and safety study are:

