Specific Aim 1: Test the hypothesis that clopidogrel monotherapy is safe following successful PCI among 100 consecutive patients with HBR and meeting the inclusion criteria (100 *active* patients, excluding patients who have been enrolled then withdrawn for various reasons such as starting an additional blood thinner, patient preference, etc.). To ensure that we have data on 100 active patients that complete their 1 month visit, we will plan to accrue up to 150 patients. The primary safety end point will be showing noninferiority of clopidogrel monotherapy in reducing ischemic events stratified by presence or absence of *CYP2C19* LOF allele (QuantStudio with Chemagic DNA extraction). All patients will receive clopidogrel (600 mg load & 75 mg maintenance) and aspirin (324 mg load & 81 mg maintenance) for the first week. Those with *CYP2C19* 2* or 3* LOF allele (*CYP2C19* LOF carriers) will be prescribed prasugrel or ticagrelor [prasugrel 60 mg load, maintenance 10 mg or 5 mg (for patients \geq 75 years or $<$ 60 kg) daily or ticagrelor 180 mg load, maintenance 90 mg twice daily (dose escalation with bolus will occur regardless of the timing of the last clopidogrel dose)]. Non-carriers (or those with inconclusive results) will continue with clopidogrel 75 mg daily maintenance dose. Aspirin will be stopped in all patients once *CYP2C19* results are available.

Specific Aim 2: Among participants enrolled in aim 1, aim 2 will determine the incidence of BARC 3 or 5 bleeding events. Other secondary endpoints are post-dismissal all-cause death, any MI up to 180 days, repeat revascularization, or any other BARC bleeding episodes.

SIGNIFICANCE

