- Design Overview.** For *Aim 1*, up to 150 participants with HBR on DAPT with clopidogrel and aspirin, who have undergone successful PCI will be stratified by the *CYP2C19* LOF allele within one week of DAPT initiation. If present, participants will be given prasugrel or ticagrelor monotherapy, and non-carriers will continue with clopidogrel monotherapy. The primary safety endpoint will be a composite of post-dismissal cardiac death/spontaneous MI <30 days or stent thrombosis <90 days of discharge. For *Aim 2*, the same subjects will undergo post-dismissal assessment for BARC 3 or 5 bleeding, all-cause death, any MI, and/or repeat revascularization up to 180 days. Informed consent followed by genotype assessment will be obtained prior to discharge. Loading dose of clopidogrel (600 mg) will be given to all patients and maintenance dose of 75 mg daily will be given, as indicated. We will allow patients to be given loading dose (324 mg) of aspirin either before or at the time of PCI. The choice of stents, access site and treatment site will be at the discretion of the treating physician (**Figure 1**).
- Clopidogrel and prasugrel/ticagrelor administration.** This study will be single-center, single-arm, open label, first-in-human, and a proof-of-concept, pilot and safety study. All participants in the first week will receive clopidogrel bolus (600 mg) and maintenance (75 mg) and aspirin bolus (324 mg, if not on aspirin) and 81mg maintenance. Participants with HBR who meet the inclusion criteria will be stratified by *CYP2C19* LOF allele. Non-carriers (or those with inconclusive results) will continue with maintenance dose of clopidogrel monotherapy at 75 mg daily. If LOF allele is present, they will be prescribed either prasugrel or ticagrelor monotherapy [prasugrel 60 mg load, maintenance 10 mg daily; ticagrelor 180 mg load, maintenance 90 mg twice daily; dose escalation with bolus regardless of timing of the last clopidogrel dose]. Prasugrel will be the preferred agent except when absolutely contraindicated (history of stroke/transient ischemic attack or active bleeding). Patients ≥ 75 years or < 60 kg will receive prasugrel at a reduced dose of 5 mg daily. If there is

Figure 1: Study Flow Chart

a relative contraindication to prasugrel (as determined by the treating physician), the participant will be given ticagrelor. Maintenance aspirin will be discontinued in both arms once genotype testing has been confirmed. (**Figure 1**).

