- Hemoglobin at time of bleeding event (obtain from chart review; not available in registry)
- Creatinine and eGFR at time of PCI
- Use of clopidogrel, prasugrel, ticagrelor
- Use of oral anticoagulant (warfarin, apixaban, rivaroxaban)

Aim 1: Detailed Approach

The objective of aim 1 is to determine if clopidogrel monotherapy following successful PCI is safe among non-carriers of CYP2C19 LOF allele. The hypothesis is that carriers of CYP2C19 LOF genotype are unable to metabolize clopidogrel effectively to an active drug that blocks P2Y12 receptors and inhibit platelet aggregation and are therefore at heightened ischemic risk following PCI. We will reduce bleeding risk by giving clopidogrel monotherapy only to non-carriers. Our approach to test this hypothesis is stratifying HBR patients after successful PCI into those with CYP2C19 LOF allele and those with inconclusive results or who are

| Schedule of Events | Day 0 | Day 1 | Day 2 | Day 3 | Day 4 | Day 5 | Day 6 | Day 7 ± 2 days | Day 30 ± 1 week | Day 90 ± 1 week |
|--|-------|-------|------------|-------|-------|-------|-------|-------------------|--------------------|--------------------|
| Stent Placement | ■ | | | | | | | | | |
| Informed Consent | | ■■■ | | | | | | | | |
| Genotype Test Blood Draw | | ■■■■ | | | | | | | | |
| Study Coordinator Call with Genotype Results & Final Medication Decision | | | ■■■■■ | | | | | | | |
| Stop aspirin and continue clopidogrel or change to prasugrel/ticagrelor | | | ■■■■■■■■■■ | | | | | | | |
| 1 st Study Coordinator Follow Up Call | | | | | | | | ■ | | |
| 2 nd Study Coordinator Follow Up Call | | | | | | | | | ■ | |
| 3 rd Study Coordinator Follow Up Call | | | | | | | | | | ■ |

non-carriers. Within first week of DAPT initiation, non-carriers will receive clopidogrel monotherapy, and prasugrel/ticagrelor will be given to patients with CYP2C19 LOF allele. The *rationale* for this aim is to individualize antiplatelet therapy and to reduce bleeding risk by stratifying P2Y12 pharmacotherapy by the CYP2C19 LOF genotype. Large number (50%-70%) of patients are non-carriers and in them clopidogrel monotherapy would suffice and the remainder will receive prasugrel or ticagrelor thereby lowering bleeding risk, cost, and unique adverse effects related to ticagrelor (e.g., bradycardia, dyspnea) or excess bleeding related to prasugrel. Recruitment should not be a challenge at Mayo Clinic, Rochester where 30% of PCI patients are HBR.

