Background. Recent randomized trials have investigated different antithrombotic strategies, including monotherapy with a P2Y₁₂ inhibitor, aiming to assess the best balance between ischemic and bleeding risks after PCI. Shortening of DAPT duration is safe and has not demonstrated an increase in the incidence of ischemic risk. The limitations of the existing trials are, 1) that DAPT is given for 1-3 months, and there is an urgent need aspirin-free P2Y12 inhibition in the first month following PCI that overlaps with high risk period for PDB, 2) TWILIGHT trial randomized higher-risk patients only after demonstrating no ischemia or bleeding for the initial 3 months following PCI thereby selecting lower-risk patients for PDB, 3) ASET pilot study included only low-risk, stable patients who were given prasugrel. Older age is one of the main drivers of bleeding and along with prior TIA/stroke, or low body weight will significantly limit the applicability of monotherapy with prasugrel. In that regard, individualizing P2Y12 therapy guided by genotyping at the time of PCI allows us to use clopidogrel with lower attendant bleeding risk among non-carriers (prevalence of 60%-70%) and limiting the use of newer P2Y12 inhibitors to the rest. Accurate assessment and prolongation of period of observation is relevant especially among participants presenting with ACS.

The central goal of Aim 2 is to study the incidence of PDB and ischemia during the first 6 months following PCI with DES.

This aim leverages the support from existing Mayo Clinic PCI database in whom all the information is routinely collected following a coronary intervention.

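### The 100 patients in Aim 1 are the whole genotype-guided cohort; only about 50 to 70 of them would be on the clopidogrel monotherapy that the hypothesis names

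*Combined protocol and SAP*

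**What the plan says.** Specific Aim 1 attaches a number to a drug: "Test the hypothesis that clopidogrel monotherapy is safe following successful PCI among 100 consecutive patients with HBR". It defines the 100 as "100 *active* patients, excluding patients who have been enrolled then withdrawn for various reasons" and sets the accrual ceiling from it: "To ensure that we have data on 100 active patients that complete their 1 month visit, we will plan to accrue up to 150 patients".

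Treatment depends on genotype. Under Design Overview: "If present, participants will be given prasugrel or ticagrelor monotherapy, and non-carriers will continue with clopidogrel monotherapy". Patients with an inconclusive result also stay on clopidogrel (Specific Aim 1, and the section on drug administration).

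The expected split is given in several places. The opening rationale has "given an approximate 50% to 70% prevalence of *CYP2C19* noncarriers", and Aim 1: Detailed Approach has "Large number (50%-70%) of patients are non-carriers and in them clopidogrel monotherapy would suffice and the remainder will receive prasugrel or ticagrelor". The Background of Aim 2 gives a narrower range, 60%-70%.

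The objective in Aim 1: Detailed Approach, and the Expected Outcomes that follow it, put the clopidogrel question for non-carriers. The Expected Outcomes of Aim 2 speak of the safety of clopidogrel monotherapy in all-comers after successful PCI. Specific Aim 1 also says that the primary safety comparison is stratified by LOF status.

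**The concern.** The number in the hypothesis and the number of patients who can inform it are not the same. A carrier takes clopidogrel only in the first week, together with aspirin, and then moves to another P2Y12 inhibitor. Such a patient never receives clopidogrel monotherapy, yet counts towards the 100.

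If the result in 100 patients is reported as the safety of clopidogrel monotherapy, two things follow. Events, or the absence of events, on prasugrel or ticagrelor are credited to clopidogrel, and the interval around the clopidogrel result looks narrower than the data allow. The all-comers phrase under Aim 2 shows that this reading is close at hand. The protocol gives the clopidogrel group no size, denominator or interval of its own.

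**Working it through.** **1. The plan's own figures.** There is no sample size calculation to reproduce: no margin, alpha, power, assumed event rate or interval width is given. The only arithmetic link is from 100 to 150. It holds if one third withdraw, since 100 / (1 - 1/3) = 150, but that third is back-calculated; the protocol states no rate. The 150 allows for withdrawals, not for carriers.

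**2. Expected number on clopidogrel among 100 active patients.** Formula: 100 x non-carrier share. The range is the central 95% of a binomial distribution with n = 100.

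| Non-carrier share | On clopidogrel | 95% range | On prasugrel or ticagrelor |
|---|---|---|---|
| 50% | 50 | 40-60 | 50 |
| 60% | 60 | 50-69 | 40 |
| 70% | 70 | 61-79 | 30 |

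This assumes that carriers and non-carriers withdraw equally often. Patients with inconclusive genotypes would add to the clopidogrel column; their share is not given.

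**3. Does accruing 150 close the gap?** Even if all 150 stayed active, the expected number on clopidogrel would be 150 x 0.5 = 75, 150 x 0.6 = 90 or 150 x 0.7 = 105. The binomial chance of at least 100 on clopidogrel would be below 0.01%, 5.6% and 84% respectively. To expect 100 on clopidogrel would take 100/0.5 = 200, 100/0.6 = 167 or 100/0.7 = 143 active patients.

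**4. What the denominator does to the interval (illustration).** With zero events, the exact upper limit is 1 - 0.025^(1/n) for a two-sided 95% interval and 1 - 0.05^(1/n) for a one-sided 95% limit.

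| n | Two-sided 95% | One-sided 95% |
|---|---|---|
| 100 | 3.6% | 3.0% |
| 70 | 5.1% | 4.2% |
| 60 | 6.0% | 4.9% |
| 50 | 7.1% | 5.8% |

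On the two-sided scale, 50 patients instead of 100 roughly doubles the limit: 7.1 / 3.6 = 2.0.

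**The case against.** The best defence is that the 100 was always the cohort. The paragraph that states the hypothesis also discloses the switch for carriers and promises stratification by LOF status. The design section sets out both treatment paths, and the split is printed several times. On that reading the cohort size is delivered, and an attentive reader is not misled about who takes what. This much stands, and it lowers the severity. It does not remove the point: the hypothesis still names clopidogrel monotherapy, its objective is about non-carriers, and the promised stratification comes without a stratum size or interval.

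Three stronger readings are tempting and are not supported.

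- *A planned precision or power is missed.* None is stated, so the limits above show only what each sample size would carry.
- *Zero events on clopidogrel could not exclude the local background rate.* Table 2 shows 5% death or MI at 30 days for 2016 and 2017. That is not the primary composite (cardiac death or spontaneous MI before 30 days, or stent thrombosis before 90 days), and the caption does not restrict the table to high-bleeding-risk patients. The 5% is also rounded, and the answer turns on the choice of limit: one-sided limits exceed it only at n = 50, two-sided limits at 50, 60 and 70.
- *Accrual stops at 100 active patients.* The protocol does not say so. It says up to 150, and the Aim 2 research design refers to the same 150 participants. Step 3 shows that the gap is likely to remain at 50% or 60% non-carriers even with all 150 active; at 70% it would probably close.

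**Conclusion.** The point holds as one about the denominator. By the protocol's own prevalence, about 50 to 70 of the 100 active patients (60 to 70 on the Aim 2 figure) would be on clopidogrel monotherapy, plus an unstated number with inconclusive genotypes. The remaining 30 to 50 would be on prasugrel or ticagrelor. The 100 describes the genotype-guided strategy and cannot serve as the denominator for a statement about clopidogrel.

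The estimate assumes that the quoted prevalence applies to these patients and that withdrawal does not depend on genotype. The illustrative limits also assume zero events.

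Severity is moderate. This is a single-arm pilot, the treatment paths are disclosed, and the remedy is a matter of wording and reporting. It should still be settled before results are known, because it determines what may be concluded about the drug named in the primary aim.

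**What to change.** Restate Aim 1 as the safety of genotype-guided, aspirin-free P2Y12 monotherapy in 100 active patients, of whom about 50 to 70 are expected on clopidogrel.

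Report the primary composite for the whole cohort and separately for the clopidogrel stratum, the latter with its own denominator and a two-sided exact 95% confidence interval. If expected precision is quoted, use the two-sided limits so that it matches the reported interval. State whether inconclusive genotypes belong to that stratum: the Aim 1 approach groups them with non-carriers, while the objective mentions non-carriers only.

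Base every conclusion about clopidogrel monotherapy on that stratum alone, and reword the all-comers statement under Aim 2 to match.

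The cost is a wider interval behind the clopidogrel claim. No extra patients, visits or procedures are needed.

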3. **Medication adherence, provision of prasugrel/ticagrelor and follow-up:** Each enrolled participant will be carefully followed, pre-dismissal education about medication compliance and potential switch to prasugrel or ticagrelor will be given to each participant. A phone call by the study coordinator informing the participant about the results of genotype will be made within the first week of PCI. Study coordinator will mail 3-month supply of prasugrel or ticagrelor to patients with CYP2C19 LOF allele and contact them for the receipt of the medication and will instruct initiation of the loading and maintenance dose. The number of remaining tablets (pill count) at 3-month follow-up will be counted and recorded to assess adherence using a drug accountability report at 3 months. Non-carriers will continue clopidogrel monotherapy. Our main aim is to ensure safety of the participants. Close monitoring and follow-up of each patient will be done. Study-related events will be assessed by the study coordinator at hospital discharge and at 1 and 3 months after PCI by telephone. If patients could not be reached by telephone after multiple attempts, the site coordinator will conduct a medical record review to assess follow-up. All cardiovascular-related end points and hospitalizations will be reviewed and adjudicated by an independent committee blinded to study groups and P2Y12 inhibitor received by the patient. Only study-related events confirmed by the adjudication committee will be included in the analysis.
4. **Trial Duration:** 90 days. This is based on the observations that the highest bleeding and ischemic risk following PCI is within first 90 days. Importantly, a post-hoc analysis demonstrated an almost 80% risk reduction for ischemic events with genotype guidance in the first 3 months after PCI.

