5. **Definitions and Role of Data and Safety Monitoring Board (DSMB):** All deaths will be considered cardiac unless a clear noncardiac cause can be ascertained. Spontaneous MI will be defined according to the fourth universal definition.²¹ Periprocedural MI (< 48 hours post-PCI) will be defined according to the 2013 definition of the Society for Cardiovascular Angiography and Interventions.²² Stent thrombosis will be defined and classified according to the Academic Research Consortium-2 definition.²³ BARC bleeding will be defined as previously reported.²⁴ All endpoints will be independently adjudicated by the clinical event committee. An independent DSMB will oversee the individual and collective safety of the patients in the study during enrollment and follow-up. To provide the steering committee with timely feedback on potential safety issues, the DSMB will review the data 3 times during the trial: (1) When the 25th patient is enrolled, (2) when the 50th patient is enrolled, (3) when the 100th patient is enrolled, and (4) when the 100th actively enrolled patient completes 1-month follow-up.
6. **Subjects**
 - a) **Inclusion Criteria:** Informed consent after successful PCI [no non-fatal MI/stroke/repeat target revascularization/bleeding/acute kidney injury] and academic research consortium-high bleeding risk (ARC-HBR) score ≥ 4 .
 - b) **Exclusion Criteria:** Chronic use of warfarin or direct oral anticoagulant (DOAC), unsuccessful PCI (see above), lesions with angiographic thrombus, prior PCI within 6 months (except for staged PCIs within the same hospitalization or within 7 days of initial PCI, in which case enrollment will occur following the final planned/staged PCI), planned PCI greater than 7 days but less than 6 months following index PCI, planned surgical intervention to treat any cardiac or noncardiac condition within 6 months (excluding transcutaneous valve interventions and pacemakers), high risk lesion/stent characteristics (>50% unprotected left main disease, bifurcation disease requiring 2 stents technique, rotational atherectomy, vein graft, unprotected left main intervention, or history of definite stent thrombosis), women of child-bearing age unless negative pregnancy test is done, life expectancy <1 year, known drug/alcohol dependence, and assessment that the patient will not be compliant with the study protocol.

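### Aim 1 rests on 100 active patients, with withdrawals dropped and replaced, while other sections point to everyone enrolled; the ischemic rate should also be reported in all enrolled patients

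*Combined protocol and SAP*

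**What the plan says.** Specific Aim 1 sets the population as 100 active patients, "excluding patients who have been enrolled then withdrawn for various reasons such as starting an additional blood thinner, patient preference, etc". Up to 150 are accrued to secure "data on 100 active patients that complete their 1 month visit". The list of withdrawal reasons is open-ended, and recruiting beyond 100 in effect replaces those who leave.

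Other places describe a wider population:

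- General Methods item 1 (Design Overview) describes Aim 1 as up to 150 participants, names no exclusion for withdrawal, and gives the endpoint: "The primary safety endpoint will be a composite of post-dismissal cardiac death/spontaneous MI <30 days or stent thrombosis <90 days of discharge".
- Specific Aim 2 takes its population as those enrolled in Aim 1. Its endpoints include all-cause death and any MI.
- The Aim 2 Research Design refers to the same 150 participants.
- General Methods item 3 says "Each enrolled participant will be carefully followed".

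The provisions closest to a rule for withdrawn patients are also in item 3. One covers patients who cannot be contacted: "If patients could not be reached by telephone after multiple attempts, the site coordinator will conduct a medical record review to assess follow-up". The other covers adjudication: "Only study-related events confirmed by the adjudication committee will be included in the analysis". The first concerns patients not reached by telephone; the second decides which events count, not whose. In General Methods item 5, the first three listed DSMB reviews are triggered by numbers enrolled, and the last falls "when the 100th actively enrolled patient completes 1-month follow-up".

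**The concern.** The pilot's main output is an ischemic event rate on early aspirin-free therapy. If membership of the analysed 100 depends on not withdrawing and on completing a visit at one month, the rate is conditioned on events after enrolment. It is then unbiased for the enrolled population only if withdrawn patients have the same risk as those who stay.

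Three features make this more than a formality.

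- A patient who dies before day 30 cannot complete the 1-month visit, and the text does not say whether that patient is active. The Significance section itself says that cardiac deaths due to MI are concentrated in the first week after PCI.
- An additional blood thinner is not defined, and an open list of reasons leaves room for withdrawals related to outcome.
- Active status is tied to one month, whereas the stent thrombosis component runs to 90 days. Handling of later withdrawals is not stated.

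A confidence interval does not show selection of this kind, and enrolling more patients does not remove it.

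**Working it through.** **The plan's own figures.** Target 100 active, cap 150 (Specific Aim 1). At the cap with exactly 100 active, 150 − 100 = 50 are left out, and 50/150 = 33.3%. Conversely, 100/(1 − 1/3) = 150. The documents state no expected withdrawal rate, so 33% is a ceiling and not a forecast.

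**Assumptions.** The documents give neither the number of withdrawals nor the event rate among withdrawn patients.

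- Active-set result: 5 events in 100. Table 2 shows 5% death or MI at 30 days in 2016 and 2017. That is not the trial's composite, and the table shows no restriction to high bleeding risk.
- m = number withdrawn: 11 (about 10% of 111 enrolled), 25 (20% of 125) or 50 (33% of 150).
- k = event rate in withdrawn divided by event rate in active: 0.5, 1, 2 or 3.

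**All-enrolled rate** = (5 + m × 0.05 × k)/(100 + m). For m = 50 and k = 3: (5 + 7.5)/150 = 8.3%.

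| m | k = 0.5 | k = 1 | k = 2 | k = 3 |
|---|---|---|---|---|
| 11 | 4.8% | 5.0% | 5.5% | 6.0% |
| 25 | 4.5% | 5.0% | 6.0% | 7.0% |
| 50 | 4.2% | 5.0% | 6.7% | 8.3% |

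The exact (Clopper-Pearson) 95% interval for 5/100 is 1.6% to 11.3%. Every entry lies inside it.

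**A higher base rate.** With 9 events in 100 (the Table 2 total at 30 days) and m = 50, the rate is (9 + 50 × 0.09 × k)/150 = 7.5%, 9.0%, 12.0% and 15.0%. The exact interval for 9/100 is 4.2% to 16.4%, so the conclusion is the same.

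**If withdrawn outcomes stay unknown.** The bounds run from 5/(100 + m), where none has an event, to (5 + m)/(100 + m), where all do.

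| m | Lower | Upper |
|---|---|---|
| 11 | 4.5% | 14.4% |
| 25 | 4.0% | 24.0% |
| 50 | 3.3% | 36.7% |

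The upper ends are implausible. They show how much rests on obtaining the outcomes, which is what record review supplies.

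**Early deaths.** As an illustration, suppose 9 of 100 enrolled patients have a qualifying event by day 30 and 3 of those events are deaths. Requiring a completed visit leaves 6/97 = 6.2% in place of 9.0%. Unlike withdrawal in general, this omission can only lower the rate.

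**The case against.** The strongest reply is that the plan does not confine itself to the active set. The Design Overview states the primary endpoint for up to 150 participants without exclusion, Aim 2 reports death and MI among those enrolled, and three of the four listed DSMB reviews count enrolled patients. All participants also enter the institution's PCI database, and outside records are to be retrieved. This stands to the extent that the documents are ambiguous between active and enrolled. It does not settle the matter, because none of these places mentions withdrawn patients or says that their events enter the Aim 1 composite.

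Four stronger readings are tempting and not supported.

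- A reader might infer that withdrawn patients' events will be discarded and that no result will include them. The sections above point the other way. The available text also breaks off within the list of monitored adverse events and lacks the supplement, so a rule may exist elsewhere.
- A reader might infer that the exclusion makes the therapy look safer than it is. Apart from deaths before the visit, nothing in the documents fixes the direction.
- A reader might call 100 and up to 150 contradictory. They are a target and a cap. Only the Aim 2 wording, which treats 150 as a fixed number, is loose.
- A reader might call the exclusion of anticoagulant starters illegitimate. It fits the stated wish to study antiplatelet monotherapy, provided the result is labelled on-treatment.

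It can also be said that some withdrawals will precede monotherapy, since consent is on day 1 and "Maintenance aspirin will be discontinued in both arms once genotype testing has been confirmed". That is correct and suggests analysing everyone who stopped aspirin. But such a set conditions on reaching the aspirin stop without an event, while the endpoint clock starts at discharge. It does not replace an all-enrolled result.

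**Conclusion.** The point holds as a cheap improvement that should be made. Specific Aim 1 states an analysis rule that conditions on post-enrolment events, other sections imply a different population, and nothing reconciles them. The bias could go in either direction and the documents do not give its size. Under the assumed 5 events in 100 active patients and 50 withdrawn, the all-enrolled rate ranges from 4.2% to 8.3% for rate ratios of 0.5 to 3; with 11 withdrawn it ranges from 4.8% to 6.0%. These shifts lie within the sampling error of 100 patients, so this alone would not overturn the pilot. The available text gives no noninferiority margin, so it cannot be said whether such a shift would change the formal conclusion. Confidence is medium, because of the incomplete text and the assumed withdrawal numbers and rate ratios.

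**What to change.** 1. Keep 100 active patients as the accrual target and as an analysis labelled on-treatment.
2. Report the primary composite in all enrolled patients beside it. Make Specific Aim 1, the Design Overview and the Aim 2 Research Design agree on the Aim 1 population, and say in advance which set carries the conclusion. All enrolled is the natural choice for a safety claim, since it does not condition on later events.
3. Count every adjudicated event before withdrawal, and every qualifying death before day 30 whether or not the 1-month visit took place.
4. Extend the record review in General Methods item 3 to withdrawn patients where consent allows: to 30 days for cardiac death and MI, and to 90 days for stent thrombosis.
5. List withdrawals by number, timing and reason. For outcomes that stay unknown, give a simple sensitivity range, such as rate ratios of 0.5 to 3 plus the none and all extremes.
6. If a set of those who stopped aspirin is wanted, report it only as supplementary, with time at risk starting at the aspirin stop.
7. Change the fixed 150 in the Aim 2 Research Design to a cap.

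The cost is a few sentences of protocol text and extra record review and adjudication, for up to 50 patients at the cap. The reported rate may turn out less favourable.
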